2. STUDY OBJECTIVES

2.1. Primary Objective

- To evaluate the efficacy and safety of orally administered nevanimibe HCl for the treatment of classic CAH

2.2. Secondary Objectives

[figure not shown]
- To assess the changes in adrenal cortical steroids and steroid intermediates
- To determine the pharmacokinetic (PK) parameters of nevanimibe and its major metabolite(s)
- To assess the PK/pharmacodynamic (PD) relationships of nevanimibe and its major metabolite(s)

3. INVESTIGATIONAL PLAN

3.1. Overall Study Design

This is a multicenter, intra-subject dose-titration open-label study of nevanimibe HCl for the treatment of classic CAH. Following a Screening Period of approximately 2-14 weeks, eligible subjects will enter a Baseline Period of approximately 2-8 weeks and then a 16-week Treatment Period. During the Treatment Period, subjects will receive nevanimibe HCl twice daily (BID) for 16 weeks. All subjects will begin dosing with nevanimibe HCl 500 mg BID. After the 4-week 500 mg BID dosing period, serum samples for 17-OHP will be obtained at Visit T2 and the nevanimibe HCl dose will be automatically up-titrated to 1000 mg BID for all subjects. Although all subjects will receive nevanimibe HCl 1000 mg BID for Weeks 5 and 6, once the 17-OHP results from Visit T2 become available, the nevanimibe HCl dose for Weeks 7 and 8 will either remain at 1000 mg BID (if the Visit T2 predose serum 17-OHP is $> 2x$ ULN) or be decreased to 500 mg BID (if the Visit T2 predose serum 17-OHP is $\leq 2x$ ULN). The dosing regimens are intended to achieve and maintain $17\text{-OHP} \leq 2x$ the upper limit of normal (ULN) (the primary endpoint) on the lowest possible dose of nevanimibe HCl while actively up-titrating if $17\text{-OHP} > 2x$ ULN. Thus, subjects who are found to have met the primary endpoint (i.e., on the previous lower dose of nevanimibe HCl) based on their most recent serum 17-OHP value will have their nevanimibe HCl dose down-titrated to the dose on which they met the endpoint. Subsequent dose adjustments will follow the same procedures. Four doses of nevanimibe HCl (500 mg BID, 1000 mg BID, 1500 mg BID, and 2000 mg BID) are available for use in the study. The study schematic is shown in Figure 1.

Figure 1: Study Schematic

3.1.1. Screening Period

After signing informed consent, subjects with classic CAH will enter the Screening Period to assess preliminary eligibility for the study based on the inclusion and exclusion criteria. In

addition, pertinent information will be collected such as past medical history, demographic data, and prior and current medications. Laboratory tests will be done as part of study eligibility.

Subjects with a serum 17-OHP $\geq 4x$ ULN (Cohort 1) at the initial screening visit (Visit S1) will proceed to the Baseline Visit (Visit B1). Cohort 1 subjects will not make any changes in their daily maintenance glucocorticoid dose throughout the study (except, for example, for emergency, stress dose requirements). Subjects with a serum 17-OHP $< 4x$ ULN (Cohort 2) AND a daily maintenance glucocorticoid dose in the suppressive range (\geq the equivalent of approximately 12 mg hydrocortisone/m² body surface area—see Appendix 3) at the initial screening visit (Visit S1) will have their glucocorticoid dose decreased by the equivalent of approximately 5 mg hydrocortisone or 1 mg prednisone or prednisolone (see Appendix 2). They will then return for Visit S2 to have their 17-OHP level rechecked approximately 2 to 4 weeks after their glucocorticoid dose was changed. If their serum 17-OHP level from Visit S2 is $\geq 4x$ ULN, they will proceed to the Baseline Visit (Visit B1). If not, the case should be discussed with the Medical Monitor; if appropriate, the subject may undergo further glucocorticoid dose adjustment and subsequent assessment of serum 17-OHP levels during the Screening Period. The Screening Period may last from approximately 2-14 weeks.

3.1.2. Baseline Period

At the Baseline Visit (Visit B1), additional laboratory tests will be done as part of study eligibility. In addition, subjects will be instructed on the use of an electronic diary (eDiary) for recording their glucocorticoid, mineralocorticoid (if applicable), and study drug doses (and, for premenopausal women, start dates of menstrual periods) during the study. The most recent serum 17-OHP level should be $\geq 4x$ ULN for all subjects prior to Visit B1. Any subject whose Visit B1 serum 17-OHP is $< 4x$ ULN should be discussed with the Medical Monitor prior to enrolling in the study. Cohort 2 subjects may require further decreases in glucocorticoid dose and subsequent assessment of serum 17-OHP during the Baseline Period (see Appendix 2). No study drug will be given during the Baseline Period. The Baseline Period may last from approximately 2-8 weeks.

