3.1.3. Treatment Period

Subjects who meet all of the inclusion criteria and none of the exclusion criteria may be enrolled into the 16-week Treatment Period. Enrollment in either Cohort 1 or Cohort 2 may be capped at the Sponsor's discretion to ensure that a sufficient number of subjects are enrolled into both cohorts.

All enrolled subjects will receive open-label active treatment with nevanimibe HCl orally starting at a dose of 500 mg BID. The first dose of nevanimibe HCl will be given at the study site at Visit T1 (Day 1; Enrollment). All subjects will receive nevanimibe HCl 500 mg BID for Treatment Period Weeks 1-4 (Day 1 to Day 28). At Visit T2 (Day 29), blood for assessment of serum 17-OHP will be collected; all subjects will have their nevanimibe HCl dose automatically up-titrated to 1000 mg BID and will remain on this dose for Weeks 5-6 (Day 29 to Day 42). The Visit T2 (Day 29) serum 17-OHP samples require ~10 days to process and results should be available before the beginning of Week 7 (Day 43).

If the Visit T2 predose 17-OHP is $\leq 2x$ ULN (primary endpoint is met), subjects will have their nevanimibe HCl dose down-titrated from 1000 mg BID to 500 mg BID starting at Week 7 (Day 43) and remain on this dose until the end of Week 10 (Day 70). If the serum 17-OHP value

obtained at Visit T2 is $> 2x$ ULN (primary endpoint is not met), the subject will continue on their current 1000 mg BID dose for Weeks 7-8 (Day 43 to Day 56) and will automatically up-titrate to 1500 mg BID for Weeks 9-10 (Day 57 to Day 70). At Visits T3 (Day 57) and T4 (Day 85), subjects whose most recent predose serum 17-OHP met the primary endpoint will remain on the nevanimibe HCl dose on which they met the endpoint. Subjects whose most recent predose serum 17-OHP did not meet the primary endpoint will have their nevanimibe HCl dose increased to the next higher dose level.

Following Visits T3 and T4, nevanimibe HCl dose adjustment will proceed in a similar manner as Visit T2. The serum 17-OHP samples require ~ 10 days to process. When the predose serum 17-OHP results are available, they will be used to titrate the nevanimibe HCl dose as follows:

- Subjects whose predose serum 17-OHP is $\leq 2x$ ULN (primary endpoint is met) will have their nevanimibe HCl dose decreased to the dose on which they most recently met the endpoint if they underwent a dose increase at their most recent treatment period site visit.

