4.2. Inclusion Criteria

Each subject must meet all the following criteria to be enrolled in this study:

1. Provision of signed and dated informed consent prior to any study-specific procedures
2. Men and women 18 to 80 (70 in the Czech Republic) years of age (inclusive) at the time of informed consent
3. Documented historical diagnosis of classic CAH due to 21-hydroxylase deficiency based on either or both of the following criteria:
 - Documented genetic mutation in the CYP21A2 enzyme consistent with a diagnosis of classic CAH
 - Historical documentation of elevated 17-OHP (e.g., in infancy or following a cosyntropin/ACTH stimulation test)
4. Serum 17-OHP \geq 4x ULN during the Baseline Period
 - Premenopausal women in the follicular phase of the menstrual cycle must have serum 17-OHP \geq 4x follicular phase ULN
 - Premenopausal women in the luteal phase of the menstrual cycle must have serum 17-OHP \geq (4x follicular phase ULN + (luteal phase ULN – follicular phase ULN))
5. Chronic glucocorticoid replacement therapy for at least 6 consecutive months prior to Screening
6. Stable glucocorticoid and mineralocorticoid regimen for at least 4 weeks prior to the Screening (S1), Baseline (B1), and Enrollment (T1) Visits
7. For subjects who undergo maintenance glucocorticoid dose adjustment between Screening and Enrollment, stable serum 17-OHP levels (adjusted as needed for menstrual cycle phase) prior to Enrollment, defined as the most recent 2 values being within 30% of each other (calculated as $100 \times (1 - (\text{smaller value}/\text{larger value}))$)
8. Female subjects of childbearing potential must consent to use two medically acceptable methods of contraception, excluding depot progesterone, throughout the study period and for 30 days after the last dose of study treatment during any sexual intercourse with a fertile male partner (in France: Fertile subjects (male and female) must consent to use two medically acceptable methods of contraception, excluding depot progesterone, throughout the study period and for 30 days after the last dose of study treatment during any sexual intercourse with a fertile partner of the opposite sex)

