7.1.2. After Visit S1

Within approximately 2 weeks after Visit S1, appropriate study site personnel should:

- Review all assessable inclusion and exclusion criteria.
- Review serum 17-OHP results (see Appendix 2).
- Contact the subject via telephone to:
 - Record AEs and update medications. If the subject is a premenopausal woman, obtain the start date of her last menstrual period.
 - If serum 17-OHP is $\geq 4x$ ULN (Cohort 1), schedule the subject for the Baseline visit, Visit B1.
 - If serum 17-OHP is $< 4x$ ULN (Cohort 2), assess the subject's maintenance glucocorticoid replacement dose in equivalent mg of hydrocortisone/m² body surface area (see Appendix 3).

- If ≥ 12 mg/m², reduce the dose by the equivalent of approximately 5 mg hydrocortisone or 1 mg prednisone or prednisolone, and schedule the subject to return for Visit S2 approximately 2-4 weeks after the dose change.
- If < 12 mg/m², discuss the case with the Medical Monitor; screen-fail the subject if no further glucocorticoid dose reduction is possible.
- Remind the subjects that on the morning of their next study visit, they should wait to take their morning dose of glucocorticoid and mineralocorticoid (if applicable) replacement until directed by site personnel at the study site.
- Remind the subjects to bring their glucocorticoid and mineralocorticoid (if applicable) containers to their next study visit.

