7.2.2. After Visit B1

Within 2 weeks after Visit B1, prior to Visit T1, review serum 17-OHP results (see Appendix 2):

- If 17-OHP is $\geq 4x$ ULN:
 - If the subject met criteria for Cohort 1 based on the S1 serum 17-OHP, the subject should return for the Enrollment visit, Visit T1, as scheduled.
 - If the subject met criteria for Cohort 2 based on the S1 serum 17-OHP, assess stability of 17-OHP.
 - For the purposes of this study, “stable” serum 17-OHP levels following a glucocorticoid dose reduction are defined as the most recent two 17-OHP levels prior to enrollment being within 30% of each other (calculated as $100 \times (1 - (\text{smaller value}/\text{larger value}))$).
 - If 17-OHP levels are stable, the subject should return for the Enrollment visit, Visit T1, as scheduled.
 - If 17-OHP levels are not stable, discuss the case with the Medical Monitor, and consider obtaining a repeat serum 17-OHP level(s). Once the repeat 17-OHP levels are $\geq 4x$ ULN and meet stability criteria, the subject may proceed to the Enrollment visit, Visit T1.

- If 17-OHP is $< 4x$ ULN:
 - If the subject met criteria for Cohort 2 based on the S1 serum 17-OHP, assess the subject's maintenance glucocorticoid replacement dose in equivalent mg of hydrocortisone/m² body surface area (see Appendix 3) and discuss the case with the Medical Monitor.
 - If ≥ 12 mg/m², with agreement of the Medical Monitor, it may be possible to reduce the dose by the equivalent of approximately 5 mg hydrocortisone or 1 mg prednisone or prednisolone. The subject should then return for an Unscheduled visit at least 2 weeks after the dose change to assess 17-OHP levels. Further management should be discussed and agreed with the Medical Monitor.
 - If < 12 mg/m², discuss the case with the Medical Monitor.
 - In the unlikely event that a subject in Cohort 1 (based on the S1 serum 17-OHP), has 17-OHP $< 4x$ ULN, discuss the case with the Medical Monitor.

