7.3.1. Visit T1 (Day 1; Week 1; Enrollment)

Prior to Visit T1, the Investigator should review whether the subject continues to be eligible for the study. If not, the subject should be failed from the study. Please note that the Visit B1 serum cortisol, A4, ACTH, total T, and 11-ketoT results, as well as the salivary hormone results, do not need to be available for the subject to proceed with Visit T1.

At Visit T1, appropriate study site personnel should:

- Record AEs and update medications.
- Review the subject's eDiary entries and reinforce instruction on the use of the eDiary as needed.
- Confirm that the subject has recorded the date and time of their last doses of glucocorticoid and mineralocorticoid (if applicable) prior to the visit using the eDiary. If not, ask the subject to record the information.
- If the subject is a premenopausal woman, confirm that she has recorded the start date of her last menstrual period using the eDiary. If not, ask her to record the information.
- Record vital signs and weight.
- Perform a complete PE.
- Within 30 minutes prior to administration of study drug and morning replacement glucocorticoid and mineralocorticoid (if applicable) doses, collect blood samples for hematology, chemistry, hormones (17-OHP, P, cortisol, A4, ACTH, total testosterone, and 11-ketotestosterone), PK, and a serum storage sample; and collect a saliva sample for 17-OHP, P, and cortisol.

- For each study visit, the first hormone sample collection that is obtained at the study site should be done between 6-10 AM (06:00-10:00), as close to 8 AM (08:00) as practicable.
- Hormones should not be collected if the subject already took their replacement glucocorticoid and/or mineralocorticoid dose that morning; instead, the sample collection and enrollment should be rescheduled for the next day or as soon as is feasible.
- Note: On days when both a salivary 17-OHP profile and saliva for 17-OHP, P, and cortisol are being collected, only single “8 AM” (“08:00”), “10 AM” (“10:00”), and “noon” (“12:00”) saliva samples should be collected.
- Collect a urine sample for urinalysis.
- For female subjects of childbearing potential only, collect a urine sample and perform a urine pregnancy test.
- Confirm that the subject meets all of the inclusion criteria and none of the exclusion criteria.
- Enroll the subject.
- Dispense study drug and instruct the subject on self-administration of study drug orally twice per day.

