7.5 Evaluation of the Primary Efficacy Endpoint

The primary efficacy endpoint, the percentage of subjects achieving predose serum 17-OHP targets at Visit T2 (Day 29), Visit T3 (Day 57), Visit T4 (Day 85), or Visit T5 (Day 113; Amendment 2), will be evaluated for the mITT population and repeated for the PPP. Achievement of the serum 17-OHP targets will be determined as follows:

-Men and postmenopausal women: 17-OHP $\leq 2 \times$ ULN

-Premenopausal women:

-Follicular phase: 17-OHP $\leq 2 \times$ follicular phase ULN

-Luteal phase: 17-OHP $\leq (2 \times \text{follicular phase ULN} + (\text{luteal phase ULN} - \text{follicular phase ULN}))$

Each subject who falls below the applicable 17-OHP target for at least one visit will be counted as a responder to treatment with nevanimibe HCl. Any subjects who prematurely terminates the study and was not categorized as responder before termination will be counted as a non-responder. The responder rate will be calculated overall and for each cohort (Cohort 1 and Cohort 2), by nevanimibe dose and overall. The clinical trial will be regarded as successful if a responder rate of at least 40% was observed for either of the two cohorts.

The 90% exact binomial confidence interval will be calculated for the responder rates. A variation of the following SAS code will be used for calculation of the confidence limits:

```
proc freq data = input-dataset;  
    tables responder / binomial(level='Yes' wilson) alpha=.1;  
    by visit;  
    exact binomial;  
    ods output BinomialCLs = output-dataset;  
run;
```

Additional summary statistics will be prepared, including summaries relative to the upper limit of normal (\times ULN) and absolute as well as relative change from baseline. The dose-response relationship may additionally be displayed graphically.

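### The outcome of a Visit B1 17-OHP below 4x ULN is left open, and the responder rule sets no condition on the pre-treatment value; both gaps push the response rate upward

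*Protocol*

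**What the plan says.** **Entry.** Protocol 4.2, criterion 4, asks for serum 17-OHP at or above "4x ULN during the Baseline Period", adjusted for menstrual phase. It names no visit within that period. Section 3.1.2 (and the same text in the Synopsis) says that a subject with a lower Visit B1 value "should be discussed with the Medical Monitor prior to enrolling in the study". Section 7.2.2 covers the same situation by cohort. For Cohort 1 it begins "In the unlikely event that a subject in Cohort 1 (based on the S1 serum 17-OHP), has 17-OHP" below 4x ULN, and the only instruction is to discuss the case. For Cohort 2 it allows a further glucocorticoid reduction and a new sample at or above 12 mg/m², and only a discussion below 12 mg/m². After Visits S1 and S2 (7.1.2 and 7.1.4) the parallel sentence goes on to "screen-fail the subject if no further glucocorticoid dose reduction is possible"; in 7.2.2 it does not.

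**Enrollment checks.** Section 3.1.3 states "Subjects who meet all of the inclusion criteria and none of the exclusion criteria may be enrolled into the 16-week Treatment Period", and 7.3 repeats this. At Visit T1, 7.3.1 tells the site: "Confirm that the subject meets all of the inclusion criteria and none of the exclusion criteria". It also says that a subject found ineligible before T1 is to be failed.

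**Response.** Under SAP 7.5 each subject who "falls below the applicable 17-OHP target for at least one visit will be counted as a responder". SAP 6.2 limits the visits to T2, T3, T4 and, under Amendment 2, T5. Neither section refers to the T1 or baseline value, and the mITT definition (SAP 4.1) has no baseline condition. The study is positive at 40% or more in either cohort.

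**The concern.** Entry at 4x ULN or more and response at 2x ULN or less are together meant to require at least a halving of 17-OHP. Two gaps weaken that.

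First, a site holding a B1 value below 4x ULN has one instruction to discuss before enrolling and another to enroll only if all criteria are met. The text that should join them gives no outcome. A subject who enters at 2.5x or 3x ULN has a much shorter way to fall.

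Second, 17-OHP results take about 10 days, so the T1 predose value is unknown when the first dose is given. A subject who validly met criterion 4 at B1 may be at target at T1 while untreated, and one later value at target is then credited to the drug.

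There is no control arm to absorb either effect. Success rests on a point estimate in cohorts drawn from about 20 to 24 subjects, so one or two subjects can decide it.

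**Working it through.** **1. The plan's own figures.** The documents give no sample-size calculation to reproduce; protocol 9.2 says none was done. The one checkable rate, from the previous Phase 2 study (protocol 3.2), is 2/10 = 20%.

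**2. Chance of being called a responder with no drug effect.** Inputs from the documents: target 2x ULN, entry floor 4x ULN, four counting visits under Amendment 2 (Amendment 1 subjects have three, so their chances are lower). Assumed: true level m constant, log-normal within-subject variation with SD s of 0.3 to 0.5, independent visits. The documents give no s.

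Per visit, p = Φ(ln(2/m)/s). Over four visits, P = 1 − (1 − p)^4.

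| True level m | s = 0.3 | s = 0.4 | s = 0.5 |
|---|---|---|---|
| 2.5x ULN | p = 0.229, P = 64.6% | p = 0.289, P = 74.4% | p = 0.328, P = 79.6% |
| 3x ULN | p = 0.088, P = 30.9% | p = 0.155, P = 49.1% | p = 0.209, P = 60.8% |
| 4x ULN | p = 0.010, P = 4.1% | p = 0.042, P = 15.6% | p = 0.083, P = 29.2% |

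**3. Excess due to entry below the floor.** An eligible subject at exactly 4x ULN also has some chance, so the cost of the entry gap is the difference in P.

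- 2.5x against 4x: 60.5, 58.8 and 50.3 points for s = 0.3, 0.4 and 0.5.
- 3x against 4x: 26.8, 33.5 and 31.6 points.

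Two such subjects in an assumed cohort of 10 change the expected rate by 2 × excess / 10: about 10 to 12 points at 2.5x and about 5 to 7 at 3x.

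**4. How far the stability rule limits this.** Criterion 7 applies only to subjects whose glucocorticoid dose was adjusted, in practice Cohort 2. It requires the last two values to be within 30%. Section 7.2 requires the last screening value to be at least 4x ULN. A B1 value of 2.5x then differs by at least 100 × (1 − 2.5/4) = 37.5% and fails. A value of 3x differs by 25% from a screening value of exactly 4x and passes; the lowest value that can pass is 0.7 × 4 = 2.8x. The 2.5x illustration is therefore relevant mainly to Cohort 1.

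**5. Already at target at T1, in a properly enrolled subject.** With a true level of 4x ULN, the chance of being at target at T1 and again at one or more of four later visits is p × P: 0.0104 × 0.041 = 0.04% at s = 0.3, and 0.083 × 0.292 = 2.4% at s = 0.5. Higher true levels give less.

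**6. Effect on the 40% rule, upper case.** Take n = 10 (four responders needed), a 20% response chance for the other subjects, and k subjects already at target, each assumed certain to be counted. Then P(positive) = P(X ≥ 4 − k), with X ~ Bin(10 − k, 0.2): 12.1% for k = 0, 26.2% for k = 1, 49.7% for k = 2. With those k kept in the denominator as non-responders it is 8.6% (k = 1) and 5.6% (k = 2). Both k and the cohort size are assumptions; SAP 2.9 sets no cohort targets.

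**The case against.** The strongest reply is that the protocol never permits enrollment below 4x ULN. A reader might infer a waiver from 3.1.2, or conclude that failing a subject is no longer provided for after B1. Neither holds. Sections 3.1.3, 4.2, 7.3 and 7.3.1 require every criterion, and 7.3.1 says that an ineligible subject is to be failed. Serum 17-OHP is not among the B1 results that 7.3.1 allows to be outstanding at T1. Since criterion 4 names no visit, a discussion followed by a repeat Baseline Period value at or above 4x ULN would satisfy it. Appendix 2, cited as the eligibility algorithm for Screening and Baseline, is a figure not reproduced in the text available, and it may state the outcome. What stands is that the narrative sections do not state it, and that for Cohort 1 they call for no repeat sample.

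A reader might also infer that Cohort 2 is the more exposed. The documents do not show this: criterion 7 is an additional check on Cohort 2, and nothing says that its values will lie just above 4x.

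Nor do the documents support a 20-point inflation from two subjects in ten. That figure assumes certain responders and ignores the chance that eligible subjects at 4x would respond anyway. The illustration also treats 2.5x or 3x as the true level, whereas a low B1 value after a screening value of at least 4x would tend to rise again. The 30% band is an entry check and not an estimate of variation on treatment.

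Finally, barring T1-at-target subjects from the primary numerator would rest on one noisy value, when the SAP's own 17-OHP baseline (3.2.1) averages T1 with the preceding value if the glucocorticoid dose was the same. This is a fair objection, and it favours a sensitivity analysis over a change to the primary rule. The per-protocol repeat is only a partial safeguard, because SAP 5.4 reserves the classification of deviations to the sponsor.

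**Conclusion.** The point holds as two separable gaps. The entry text after Visit B1 is unresolved against criterion 4 and the enrollment checks, and the responder rule can credit the drug with a subject who was at target before the first dose. The direction is upward in both cases; the size cannot be fixed from the documents.

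On the stated assumptions, entry below the floor costs about 50 to 60 points of false-response probability per subject at 2.5x ULN and about 27 to 34 at 3x. The second gap is small if criterion 4 is enforced: at most about 2.4% of subjects whose true level is 4x ULN or more. The entry text therefore matters most. Because subjects can meet criterion 4 and still be at target at T1, correcting the entry text alone does not close the second gap.

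**What to change.** **Protocol.** Reconcile the Synopsis, 3.1.2 and 7.2.2 with criterion 4 and with 3.1.3, 7.3 and 7.3.1. State the outcome of the discussion for each cohort, so that no subject is enrolled without having met criterion 4 in the Baseline Period. Check that Appendix 2 says the same.

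**SAP 7.5.** Keep the primary rule. Add, by cohort, the number of subjects whose T1 predose value already meets the applicable target, and the number whose SAP-defined baseline does. Pre-specify a sensitivity analysis of the responder rate that keeps these subjects in the denominator and counts them as non-responders, and state whether the 40% conclusion is unchanged.

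**Cost.** Wording changes in both documents, one extra table, and possibly one or two more screen failures. No new data are needed, since the T1 predose and preceding samples are already scheduled.
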